2.2 Analysis sets

Patients who did not sign an informed consent form will be excluded from all analysis sets. All screened patients will be used in selected outputs.

2.2.1 Full Analysis Set

The Full Analysis Set (FAS) includes all patients who received at least one dose of study treatment (eltrombopag or cyclosporine).

2.2.2 Safety Set

The Safety Set includes all patients who received at least one dose of study treatment (eltrombopag or cyclosporine).

2.2.3 Per-Protocol Set

The Per-Protocol Set (PPS) includes the patients in the FAS who had no major protocol deviations.

The list of protocol deviations in [Table 2-2](#) will lead to exclusion of the patient from the PPS.

Table 2-2 Protocol deviations leading to exclusion of patients from PPS

PD description	Protocol deviation ID
Informed consent not obtained	INCL01
SAA characterization not met	INCL03
Evidence of clonal hematologic bone marrow disorder on cytogenetics*	EXCL02
Prior immunosuppressive therapy with cyclosporine, alemtuzumab, rabbit or horse ATG and thrombopoietin receptor (TPO-R) agonists.	EXCL03
Hypersensitivity to eltrombopag or its components	EXCL04
Administration of an investigational drug within 30 days or 5 half-lives, whichever is longer, preceding the first dose of study treatment	EXCL11
Eltrombopag starting dose not correct	TRT01
Cyclosporine starting dose not correct	TRT02
Failure to withdraw eltrombopag despite various reasons	WTH02
Patient impacted by COVID19	OTH02,-03,-04,-06 & TRT10,-11

*In addition the 4 patients who were enrolled and then discontinued from the study based on discrepancies between the local and central bone marrow assessment will be excluded – Using discontinued study with reason “Technical problems”

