5.2 Inclusion criteria

Patients eligible for inclusion in this study have to meet **all** of the following criteria:

1. Patient has signed the Informed Consent (ICF) prior to any screening procedures being performed.
2. Patient is male/female ≥ 18 years old at the time of informed consent and able to swallow a tablet.

3. Patient has SAA characterized by:
 - a. Bone marrow cellularity <30% (excluding lymphocytes) and
 - b. At least two of the following (peripheral blood):
 - Absolute neutrophil count <500/ μ L
 - Platelet count <20 000/ μ L
 - Absolute reticulocyte count <60 000/ μ L
4. Normal ECG defined as the following as determined via the mean of a triplicate ECG
 - Resting heart rate
50-90 bpm
 - QTcF at screening <450 msec (for male patients), <460 msec (for female patients)

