5.3 Exclusion criteria

Patients eligible for this study must not meet **any** of the following criteria:

1. Diagnosis of Fanconi anemia.
2. Evidence of a clonal hematologic bone marrow disorder on cytogenetics by central review.
3. Prior immunosuppressive therapy with cyclosporine, alemtuzumab, rabbit or horse ATG and thrombopoietin receptor (TPO-R) agonists.
4. a. Hypersensitivity to eltrombopag or cyclosporine or their components.
b. Contraindications to cyclosporine.
5. AST or ALT >3 x ULN.
6. Serum creatinine, total bilirubin, or alkaline phosphatase >1.5 x ULN.
7. Patient with liver cirrhosis.
8. a. Infection not adequately controlled with appropriate therapy.
b. Patients who are human immune deficiency virus (HIV), hepatitis C virus or hepatitis B surface antigen (HBsAg) positive. HCV-RNA negative patients are allowed to be enrolled.
9. Moribund status or concurrent hepatic, renal, cardiac, neurologic, pulmonary, infectious, or metabolic disease of such severity that it would preclude the patient's ability to consent, be compliant with study procedures, tolerate protocol therapy, or patients with less than 3 months of life expectancy.
10. Patients with cancer who are not considered cure, are on active chemotherapeutic treatment or who take drugs with hematological effects.
11. Administration of an investigational drug within 30 days or 5 half-lives, whichever is longer, preceding the first dose of study treatment.
12. Pregnancy statements and contraception requirements:

Pregnancy or nursing (lactating) women

Women of child-bearing potential, defined as all women physiologically capable of becoming pregnant (or female partners of male patients), **unless** they are using highly effective methods of contraception during dosing and for 3 months after stopping medication. Highly effective contraception methods include:

- Total abstinence (when this is in line with the preferred and usual lifestyle of the patient. Periodic abstinence (e.g., calendar, ovulation, symptothermal, post-ovulation methods) and withdrawal are not acceptable methods of contraception)
- Female sterilization (have had surgical bilateral oophorectomy with or without hysterectomy), total hysterectomy, or tubal ligation at least six weeks before taking study treatment. In case of oophorectomy alone, only when the reproductive status of the woman has been confirmed by follow up hormone level assessment

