6.1.3 Rescue medication

Transfusions with platelets and/or red blood cells should be limited during study, however must be given, when medically necessary as described in [Section 6.4.1](#).

Treatment with romiplostim or any ATG is not allowed in the study.

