6.4.3.1 Eltrombopag

Patients must abstain from using investigational or not marketed drugs without a well-known safety profile and from using prohibited prescription or nonprescription drugs within 7 days or 5-half-lives (whichever is longer) prior to the first dose of study treatment and until completion of follow-up procedures.

Patients must abstain from taking herbal supplements within 7 days (or 14 days if the drug is a potential enzyme inducer) or 5-half-lives (whichever is longer) prior to the first dose of study treatment until completion of the 30-day follow-up visit.

Any other TPO-R agonists are prohibited during this study (e.g., N-plate [romiplostim]).

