10.1.3 Per-Protocol set

The Per-Protocol Set (PPS) includes the patients in the FAS who had no major protocol deviations.

Oncology standards for protocol deviations **potentially** leading to exclusion from the PPS are:

- If the protocol deviation is very likely to confound the scientific analysis of the primary efficacy endpoint(s) or if it precludes any meaningful efficacy measurement.
If it is in direct conflict with the analysis set definition given in the title of the study (i.e. patient diagnosis, stage of disease or use of prior treatment dose not correspond to the intended patient population to be studied).

Note that patients who were enrolled and then discontinued from the study based on discrepancies between the local and central bone marrow assessment for exclusion criterion 2 will be excluded, this will ensure that only patients in the target population are included in the PPS analyses

- If documentation of pre-baseline disease progression is required and is missing.
- Treatment differs from treatment assigned
- Patient compliance as defined as patient being evaluated for primary efficacy endpoint at least once. Patient who discontinue prior to the first efficacy assessment due to adverse events, including death, will be included.

Protocol deviations leading to exclusion from the PPS will be specified in the study Statistical Analysis Plan (SAP) based on codes provided in the DHP.

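### SAP Table 2-2 has no clear entry for prohibited on-study ATG or TPO-R agonist use, nor for Fanconi anemia, so the supportive PPS response rates could include responses reached after prohibited active therapy

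*SAP*

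**What the plan says.** SAP 2.2.3 defines the PPS as FAS patients without major protocol deviations and then makes that operational: "The list of protocol deviations in [Table 2-2](#) will lead to exclusion of the patient from the PPS". Table 2-2 contains INCL01, INCL03, EXCL02, EXCL03, EXCL04 (eltrombopag hypersensitivity only), EXCL11, TRT01, TRT02, WTH02 and a group of COVID-19 codes. A footnote adds the 4 patients discontinued because local and central marrow results disagreed. The EXCL03 row reads "Prior immunosuppressive therapy with cyclosporine, alemtuzumab, rabbit or horse ATG and thrombopoietin receptor (TPO-R) agonists".

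The protocol also restricts these drugs after entry. Section 6.1.3 says "Treatment with romiplostim or any ATG is not allowed in the study", and section 6.4.3.1 says "Any other TPO-R agonists are prohibited during this study". The first exclusion criterion in section 5.3 is "Diagnosis of Fanconi anemia".

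Protocol 10.1.3 lists standards that may potentially lead to PPS exclusion. One concerns confounding ("If the protocol deviation is very likely to confound the scientific analysis of the primary efficacy endpoint(s"). Another concerns a diagnosis that conflicts with the population named in the study title, which is acquired SAA. The section leaves the final list to the SAP, using codes from the data handling plan (DHP).

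**The concern.** The same drug is treated differently according to when it was given. ATG or a TPO-R agonist before entry removes a patient from the PPS. ATG or romiplostim given during the study, against the protocol, has no entry in the table. The second case bears more directly on the endpoint. SAP 2.5.1 counts any CR or PR on or before the 6-month visit as a response and has no rule for responses that follow prohibited therapy.

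The protocol's own background figures show that ATG-based treatment is active enough to matter. Rabbit ATG with cyclosporine gives 30 to 35% (section 2.2), and horse ATG with cyclosporine and eltrombopag gave 79.3% at 6 months (section 1.1). The success threshold here is 30%. Non-responders remain on study until 6 months (section 4.1), so there is time for such a deviation to occur.

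The PPS repeats the response rate by 6 months (SAP 2.5.2) and by 3, at 12 and at 24 months (SAP 2.6.1). A reader will take it as the rate among on-protocol patients in the target disease, and the current list does not secure that meaning.

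**Working it through.** **Step 1. Compare the list with the rules.**

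- Pre-entry ATG or TPO-R agonist: prohibited by exclusion criterion 3; in Table 2-2 as EXCL03.
- On-study ATG or romiplostim: prohibited by protocol 6.1.3; no entry.
- On-study TPO-R agonist other than eltrombopag: prohibited by protocol 6.4.3.1; no entry.
- Fanconi anemia: prohibited by exclusion criterion 1, which would be EXCL01 by the table's numbering; no entry. INCL03 does not stand in for it. Inclusion criterion 3 tests marrow cellularity ("Bone marrow cellularity <30% (excluding lymphocytes) and") and blood counts, not whether the disease is acquired or inherited.

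The table is not confined to entry criteria, since WTH02 and the COVID-19 codes concern events on study.

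**Step 2. Reproduce the plan's thresholds.** With prior Beta(0.25, 1), P(ORR ≤ 20%) is the Beta(0.25 + r, 1 + n − r) distribution function at 0.20. For 15/50 this gives 0.0538, and for 17/54 it gives 0.0272. Both agree with SAP Table 3-1.

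**Step 3. PPS size.** The SAP reports 54 enrolled patients and 4 named removals. If all 54 are in the FAS, the PPS is at most 54 − 4 = 50.

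**Step 4. Effect of excluding k such responders.** An excluded patient leaves both numerator and denominator, so the rate becomes (r − k)/(50 − k). For one patient the fall is r/n − (r − 1)/(n − 1) = (n − r)/[n(n − 1)]. At 15/50 this is 35/2450 = 1.4 points; at 20/50 it is 30/2450 = 1.2 points. The values of k below are assumptions.

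| PPS before | k = 1 | k = 2 | k = 3 |
|---|---|---|---|
| 15/50 = 30.0% | 14/49 = 28.6% | 13/48 = 27.1% | 12/47 = 25.5% |
| 17/50 = 34.0% | 16/49 = 32.7% | 15/48 = 31.3% | 14/47 = 29.8% |
| 20/50 = 40.0% | 19/49 = 38.8% | 18/48 = 37.5% | 17/47 = 36.2% |

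Each patient removed costs between 1.2 points (20/50 to 19/49) and 1.6 points (13/48 to 12/47). Taking 30% as a benchmark only, the PPS rate falls below it at k = 1 from 15/50 and at k = 3 from 17/50. From 20/50 it stays above 30% for k up to 3.

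**The case against.** The case for leaving the list alone has several parts.

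- *There is no contradiction with the protocol.* Section 10.1.3 speaks of potential grounds and delegates the list to the SAP. This stands: a narrower list is a permitted choice. The gap is that the choice leaves out a deviation fitting the protocol's own confounding standard and gives no reason.
- *Other wording may already cover these patients.* The PPS is limited to patients without major deviations. Protocol 6.3.1.2 requires eltrombopag to be stopped for significant non-compliance, so a patient given prohibited ATG and left on eltrombopag might fall under WTH02. This stands in part. WTH02 does not name prohibited therapy, its scope depends on a DHP that is not available here, and it would miss a patient whose eltrombopag was withdrawn but whose response still counts.
- *The deviation would be visible anyway.* Concomitant medications are summarised and listed (SAP 2.4.2), as are protocol deviations (SAP 2.4.3). This stands: a reader could find such patients and recount, so it would be wrong to infer that the reporting hides them. The PPS estimate itself would still include them.
- *The scenario is hypothetical.* No document reports on-study ATG, romiplostim or a Fanconi case. This stands.
- *The Fanconi part is thin.* The criterion applies at entry, and the documents do not say how a diagnosis made later would be coded. This stands, and makes that part minor.
- *The primary analysis is done.* Its database lock was 09-Dec-2020 and the primary CSR has been written, so changing PPS membership now is post hoc in an open-label study. This stands, and governs how the change must be labelled.

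**Conclusion.** The point holds as a gap in a supportive analysis set. Read as the operative list, Table 2-2 does not clearly remove a patient who responded after prohibited on-study ATG or TPO-R agonist use, or a patient with Fanconi anemia. The PPS response rates could then include responses that the regimen did not produce. If such therapy were given mainly to patients doing poorly, the bias would be upward.

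Two stronger readings are not supported. A reader might infer that trial success could turn on this list. It could not: success is judged on the FAS (protocol 10.4.2), with at least 17 of 54 required (SAP section 3), and no edit to Table 2-2 changes that count. A reader might also put the effect at 2.0 to 2.5 points per patient (1/50 to 1/40). That is the effect of recoding a responder as a non-responder with the denominator fixed. Exclusion from a PPS of 50 gives about 1.2 to 1.6 points.

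These sizes assume a PPS of 50, 15 to 20 responders before removal, and one to three affected responders. The true number affected is not in the documents and may be zero.

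**What to change.** For the final analysis, add two entries to SAP Table 2-2:

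1. On-study use of ATG, or of a TPO-R agonist other than the study drug, before the response assessment. Identify patients from the deviation code if the DHP has one, otherwise from the concomitant medication eCRF. State which assessment is meant, because the PPS serves several time points.
2. As a minor addition, EXCL01 (Fanconi anemia).

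Report how many patients each entry removes; a count of zero is itself informative. Record the change in SAP section 4 as made after the primary analysis, and show the PPS results under the current list alongside.

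The cost is small: two table rows, a search of data already collected, and one extra set of PPS estimates. The drawback is a PPS that may be slightly smaller and may differ from the one in the primary CSR, which is why both versions should be shown.

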7.1.7 Follow up for safety evaluations

Patients will have safety evaluations and efficacy evaluations for the duration of the study.

All patients who are responders by 6 months will continue to have safety and efficacy evaluations up to 24 months.

All patients who are non-responders by 6 months must have safety evaluations 30 days after the last dose of study treatment and then discontinue from the study

Data collected should be added to the Adverse Events eCRF and the Concomitant Medications eCRF.

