1.1 Study design

The study design is shown in [Figure 1-1](#) and [Figure 1-2](#).

This is an interventional, phase II, single-arm, multicenter, open-label, study to investigate the efficacy and safety of the combination of eltrombopag and cyclosporine in treatment-naïve adult patients with severe aplastic anemia (SAA) as first line therapy administered for 6 months, with an additional 18 months follow-up for responders for cyclosporine tapering and duration of response until relapse or 24 months whichever is earlier.

At 6 months, **responders** will discontinue eltrombopag and start to taper cyclosporine until 24 months. Responders who are no longer responding at 6 months and **non-responders** will discontinue the treatment and study at 6 months and will be followed-up for 30 days. Responders who relapse prior to 24 months will discontinue cyclosporine and study, and will be followed-up for 30 days.

Responders who relapse and non-responders already in the follow-up under the previous protocol version will be discontinued from the study within 30 days of the approval of the protocol amendment.

The lack of availability of anti-thymocyte globulin (ATG) in several countries has left a large proportion of patients with SAA with limited treatment options and poor outcome. In this context, the combination of cyclosporine and eltrombopag, 2 therapies with different modes of action, is an attractive therapeutic option to address this unmet medical need. Cyclosporine acts as an immunosuppressant and eltrombopag acts as a stimulator of bone marrow progenitor cells.

Fifty (50) patients are planned to be enrolled.

Figure 1-1 Study design under protocol amendment 1

Under protocol amendment (PA) 1 (4 phases: Treatment 1; Treatment 2; Follow-up; post-treatment follow-up)

[figure not shown]
[figure not shown]

Figure 1-2 Study design under protocol amendment 2

Under PA2 (2 phases: Treatment 1 and Treatment 2)

* Follow-up for duration of response until relapse or Month 24 whichever is earlier for responders only who did not relapse prior to Month 6

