Due to COVID19 situation some patients may have local instead of central lab results for scheduled visits. For all patients, local results (including the visit window period) will be used if all 4 results of the efficacy parameters (hemoglobin, neutrophils, reticulocytes, platelets) from the central laboratory are not available for a scheduled visit.

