2.5.2 Supportive analyses

The ORR **by** 6 months (primary analysis) will be repeated on the PPS.

The ORR **by** 6 months (primary analysis) will also be summarised by age sub-groups and/or ethnicity using the FAS and/or PPS.

The ORR **at** 6 months will be summarised using the FAS as follows:

- The overall hematologic response will be calculated at 6 months (based on assessment at 6 months visit and the previous visit at least 7 days apart) based on the evaluable patients (i.e., patients for whom data is available at 6 months). Thus if a patient has missing laboratory parameters at 6 months or the prior visit at least 7 days apart required to calculate CR or PR, or if the patient discontinued earlier than 6 months, then the patient will be considered as a non-responder.
- ORR_a6 = Number of patients who achieved hematologic response at 6 months/Number of patients in the FAS.

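### The COVID exclusion from the Per-Protocol Set has no printed time window, so after month 6 it can in practice remove only responders from the supportive response rates by 3 and by 6 months

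*SAP*

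**What the plan says.** SAP 2.2.3 states that the deviations in Table 2-2 "will lead to exclusion of the patient from the PPS". One entry is "Patient impacted by COVID19", tied to six deviation codes. Neither the entry nor the text around it gives a date, a visit or an endpoint to which it is limited.

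The same PPS serves several endpoints. SAP 2.5.2 says that the response rate by "6 months (primary analysis) will be repeated on the PPS". SAP 2.6.1 does the same for the rate by 3 months and for the rates at 12 and 24 months.

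Time on study depends on response. In SAP 1.1, non-responders and responders who have lost their response "will discontinue the treatment and study at 6 months and will be followed-up for 30 days". Protocol 7.1.7 says: "All patients who are responders by 6 months will continue to have safety and efficacy evaluations up to 24 months". For patients from before the amendment, SAP 1.1 adds that "non-responders already in the follow-up under the previous protocol version will be discontinued from the study within 30 days" of its approval.

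Under SAP 2.5.1 a patient is a responder if response is reached by the 6-month visit. Stopping early or missing data after a first response does not undo that.

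**The concern.** A per-protocol exclusion should not depend on the outcome being measured. Here the chance of being caught by the COVID entry depends on how long a patient is observed, and observation beyond month 6 depends on having responded. A responder whose taper is disrupted in the second year could be dropped from an analysis of response by month 6 that was settled long before. A non-responder who enrolled on the same day has already left and cannot be dropped that way.

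At stake is how the supportive analysis is read. A PPS rate lowered by this mechanism could look like fragility around the 30% threshold when it reflects only who was still on study.

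The reports could also disagree. Protocol 10.5.1 has the rate by 3 months reported in the 6-month report and again in the 24-month report. A COVID deviation after the cut-off for the first report could change the PPS figure in the second, although no endpoint data had changed.

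**Working it through.** **Inputs from the documents**
- 54 patients enrolled, enrolment complete on 11-May-2020, primary lock on 09-Dec-2020 (SAP 1).
- 31 patients enrolled by 05-Oct-2018 (Protocol, rationale for Amendment 2), so 54 − 31 = 23 enrolled later.
- 4 patients with discrepant marrow results are excluded from the PPS (SAP Table 2-2, footnote). With no other exclusions (assumption), the PPS before the COVID entry is 54 − 4 = 50.
- Success needs an observed rate of at least 30% and a posterior probability below 10% that the true rate is 20% or less, with a Beta(0.25, 1) prior (SAP 3 and 6.3.1).

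**Not in the documents:** the number, dates or response status of COVID-affected patients. All values of k and q below are assumptions.

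**1. The plan's own figures.** The exact binomial tail gives 0.9460 for at least 15/50 and 0.9235 for at least 17/54 at a true rate of 40%. Both match SAP Table 3-2. The plan gives no figure for the COVID exclusion.

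**2. Direction of the post-month-6 component.** With x responders among n patients, removing k responders and no non-responders changes the rate from x/n to (x − k)/(n − k). The fall is

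x/n − (x − k)/(n − k) = k(n − x) / [n(n − k)],

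which is positive whenever 0 < k ≤ x < n.

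**3. Illustration from an assumed 20/50 = 40.0%**

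| k removed | Rate | Fall (points) |
|---|---|---|
| 2 | 18/48 = 37.5% | 2.5 |
| 4 | 16/46 = 34.8% | 5.2 |
| 6 | 14/44 = 31.8% | 8.2 |

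None of these falls below 30%. From 17/50 = 34.0%, removing 3 gives 14/47 = 29.8%, which does.

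**4. Adding exclusions in months 0 to 6.** Let p be the true rate, q1R and q1N the chances of COVID exclusion in months 0 to 6 for responders and non-responders, and q2 the chance after month 6 (responders only). The expected PPS rate is

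p(1 − q1R)(1 − q2) / [p(1 − q1R)(1 − q2) + (1 − p)(1 − q1N)].

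For p = 40%:
- With q1R = q1N, q2 of 10%, 20% or 30% gives 37.5%, 34.8% or 31.8%.
- With q1R = q1N and q2 = 0, the rate stays at 40.0%.
- With q1R = 10% and q2 = 20%, the fall is cancelled when 1 − q1N = 0.9 × 0.8 = 0.72, that is q1N = 28%. With q1N = 40% the rate rises to 44.4%.

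**5. Effect on the criteria if they are read off the PPS** (n = 50, true rate 40%, no early exclusions). Summing over the binomial number of responders and the binomial number removed, both criteria are met with probability 0.946, 0.861, 0.747 and 0.599 for q2 of 0, 10%, 20% and 30%.

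**6. Rates at 12 and 24 months.** Let r be the share of month-6 responders still responding at the later visit, unrelated to COVID exclusion. Without the exclusion the expected rate is pr. With it, the rate is p(1 − q2)r / (1 − p·q2), lower by the factor (1 − q2)/(1 − p·q2). For p = 40% and q2 = 20% that is 0.80/0.92 = 0.87. Excluding up to the 12- or 24-month visit therefore keeps the asymmetry, because the non-responders remain in the denominator.

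**The case against.** The strongest reply is that a short table label is not the whole rule. The six codes are defined in a data handling plan that was not supplied, and may already carry a window or a severity condition. Nothing available shows that a missed or remote visit late in the taper would trigger any of them. This stands, and it makes the point conditional on what the codes mean.

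A reader might infer that the PPS rate is biased downward overall. The documents do not support that. The 23 later patients include some who may have been in their first six months in 2020, and they could be excluded whatever their response. SAP 2.5.1 itself expects disruption then: "Due to COVID19 situation some patients may have local instead of central lab results for scheduled visits", and central testing is used only in the first six months. Response also needs two consecutive scheduled measurements, so early disruption could favour non-response, and excluding such patients would raise the PPS rate.

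A reader might also infer an undeclared departure from the protocol, since SAP 4 does not list this exclusion. That is not supported either. Protocol 10.1.3 names several grounds that may lead to exclusion, of which confounding of the primary endpoint is only one, and leaves the final list to the SAP.

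One PPS for all endpoints is a common convention, and late disruption does bear on the 12- and 24-month rates. The local-laboratory rule covers missing results only, so it does not make the whole exclusion redundant. The PPS would also be read against the FAS. If the 4 marrow-discrepancy patients were non-responders (assumption), the FAS rate is 20/54 = 37.0%, and the illustration shows differences of +0.5, −2.3 and −5.2 points.

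None of this explains why an event after month 6 should remove a patient from an endpoint already settled.

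**Conclusion.** The point holds in a limited form. As printed, the COVID entry has no window, and a COVID exclusion triggered after month 6 can remove only responders, apart from any non-responder caught in the 30-day safety follow-up. That component can only lower the PPS rates by 3 and by 6 months. At 12 and 24 months the same asymmetry lowers the expected rate if exclusion is unrelated to later response.

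The size is unknown. The falls of 2.5 to 8.2 points assume a PPS of 50, 20 responders and 2 to 6 late exclusions, and compare with a PPS limited to month 6, not with the FAS. The net effect of all COVID exclusions could go either way.

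The efficacy decision uses the FAS and does not change. What is affected is the reading of a supportive analysis, and possibly agreement between the two reports.

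**What to change.** In SAP Table 2-2, limit the COVID codes as follows:
- **Rates by 3 and by 6 months:** exclude only for a COVID deviation dated on or before the 3-month or 6-month visit respectively, and only if it affected dosing or left response parameters missing after the local-laboratory rule.
- **Rates at 12 and 24 months:** use the same month-6-limited PPS. Do not exclude responders for later COVID deviations while non-responders stay in the denominator. Report the responders affected after month 6 separately or in a sensitivity analysis. This matters because SAP 2.6.1 follows the at-6-months method, under which missing results count as non-response.
- **Data handling plan:** if the codes already carry such a window, state it in Table 2-2. The 3- and 6-month part of the point is then closed.

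The cost is a line or two in Table 2-2, a date condition in the analysis-set program, and one extra listing or sensitivity table. PPS membership would differ slightly between the 3-month rate and the others. Because the primary report is already written, its PPS rates should be rerun under the new rule, with a footnote in the final report if membership changes.
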